Intervening in Food Insecurity to Reduce and Mitigate (InFoRM) Childhood Obesity

National Clinical Trial (NCT) Identified Number: NCT05586269

Principal Investigator: [name], MPH

Sponsor: Boston Children's Hospital

2023-01-23

Description: Study protocol and analysis plan

STUDY PROTOCOL

BACKGROUND

“Food is medicine” focuses on the integration of food and nutrition interventions, also referred to as nutrition security, in the healthcare system. Medically tailored meal (MTM) programs have been shown to reduce food insecurity, improve dietary quality, and decrease healthcare utilization for adults with chronic illnesses.^{4,5} This evidence has paved the way for Medicaid in some states, including MA, CA, NY, and MI, to reimburse MTMs and similar nutrition support for eligible adults. Meal kits with step-by-step home preparation instructions, which further provide nutrition education alongside healthy food, are an innovative adaptation to MTMs. EatWell, a Boston-based company, provides healthy, culturally tailored meal kits with fresh ingredients and easy-to-follow recipes to food-insecure populations. Despite the evidence in adults, there is a major knowledge gap and a lack of evidence to support nutrition security interventions such as meal kits to treat obesity and nutritional disorders in children and families. But the potential is substantial since childhood is an important period where health behaviors such as diet can set the stage for cardiometabolic health over the lifespan.^{3,4}

SPECIFIC AIM

Pilot a 6-week meal kit delivery program using a randomized, cross-over trial design in 30 families with children (6-11 years old) with food insecurity and obesity.

DESIGN

Study Design & Population: Drawing from children who receive primary care at Boston Children’s at Martha Eliot Health Center (Martha Eliot), we will recruit dyads (child + primary caregiver/parent). Martha Eliot serves families who are predominantly publicly insured (~75%) and self-identify as Hispanic or Latinx (~70%). Prior to the pandemic, ~12% of families at Martha Eliot reported food insecurity. Children with BMI $\geq 95^{\text{th}}$ percentile and a positive screen for food insecurity screened routinely on the 2-item Hunger Vital Sign™⁵ will be eligible. We will use a randomized, cross-over trial study design. We have chosen this design due to concern about the ethics of withholding a potentially beneficial intervention to a vulnerable population of families with unmet social needs. We have also chosen this design because it provides a randomized control trial method.

Inclusion Criteria: Dyads (also referred to as “participants”) including children who are 1) 6 to 11 years old 2) with a BMI $\geq 95^{\text{th}}$ percentile 3) screened positive on the 2-item Hunger Vital Sign™ 4) in a household of ≤ 5 people, 5) living with an English and/or Spanish-speaking caregiver and 6) living within the EatWell delivery map boundaries in the greater Boston area.

Exclusion Criteria: Participants (either child or parent) with a history of 1) food allergies or intolerance to dairy, gluten, soy, or any potential component of the meal kit; 2) malabsorptive intestinal disease (e.g., Crohn’s disease, celiac disease); 4) type 1 or 2 diabetes; 5) solid tumor or bone marrow transplant; or 6) enteral tube dependence.

Intervention: EatWell meal kits will be delivered once weekly to households for 6 weeks. Healthy meal kits are developed by a trained chef and registered dietician. Each household will receive one meal kit per week.

Randomization: Participants will be randomized to one of two intervention sequences:

- A) Meal kit intervention without delay followed by newsletter + pantry referral (standard of care)
- B) Newsletter + pantry referral followed by meal kit intervention after a delay of 8 weeks

The printed newsletter lists additional local food assistance resources.

Sampling/Power: A pilot study is defined as “a small-scale test of the methods and procedures to be used on a larger scale.”⁶ We will assess the feasibility of an intervention to be refined for a larger-scale RCT. We will also assess the short-term impact of the pilot intervention. The planned sample of 30 dyads (a total of 30 children + 30 caregivers) is based on practical considerations, including participant flow, budgetary constraints, and the number needed to reasonably evaluate the feasibility of the intervention.

Study Visits: We have outlined the three study visits (**Table 1**), which will initially collect baseline demographic, medical and dietary history, provide questionnaires, and measure weight and height. Follow-up visits will be

conducted between Periods 1 and 2 (6 weeks), and then after Period 2 (14 weeks). Follow-up visits will include dietary assessments and questionnaires and measure the children's weight and height.

Table 1. Outline of study visits and measures collected

Study Visit	Measures
V1, in-person: Participants will meet with the study physician and research assistant to review eligibility criteria and obtain informed consent (including assent from eligible participants).	
Baseline demographics: age, sex, insurance type, and race and ethnicity.Medical history: to assess for underlying gastrointestinal, endocrinologic, cardiometabolic, allergic conditions, and current and past medication history.Dietary assessmentQuestionnairesAnthropometrics: weight, height, and calculated BMI for each child
V2, in-person: Participants will meet with the research assistant.	
Dietary assessmentQuestionnairesAnthropometrics
V3, in-person: Participants will meet with the study physician and research assistant.	
Dietary assessmentQuestionnairesAnthropometrics

Study Outcomes: The primary, intention-to-treat analysis will examine the feasibility of the meal kit delivery intervention. We will assess **primary outcomes** of feasibility of recruitment, randomization, retention, adherence, protocol, and assessments.⁷ Primary outcomes will be assessed throughout the study. We will assess **secondary outcomes** of the intervention's short-term impact, which will include questionnaires on food insecurity and anthropometrics. Secondary outcomes will be assessed at Visits 1-3. We will additionally include the assessments we plan to include in a future RCT, including diet quality, mealtime behaviors, and perceived stress.

Analysis Plan: Consistent with the goal of pilot studies, our analysis will be mainly descriptive.⁸ However, we will collect secondary outcomes including severity of household food insecurity and child BMI. We will collect and describe dietary quality and mealtime behaviors, among other assessments, and EHR data. We will present secondary outcomes as means (with standard deviations) or proportions.

ADVERSE EVENT CRITERIA AND REPORTING PROCEDURES

This proposal seeks to pilot and evaluate implementation of a nutrition security intervention using weekly meal kit delivery in food-insecure families with children 6 to 11 years old with obesity. This intervention will be tested at Boston Children's at Martha Eliot Health Center. This proposed study will leverage the existing partnership with EatWell meal kits. EatWell meal kits are prepared at Commonwealth Kitchen in Boston, MA, which adheres to a rigorous food safety program and complies with National Restaurant Association ServeSafe requirements and FDA requirements, and other applicable regulations, in addition to being regularly inspected by the City of Boston. The meal kits occasionally contain gluten and diary, but do not contain tree nuts or peanuts, although they are manufactured in a shared use facility and the product may contain trace amounts of Milk, Eggs, Fish, Shellfish, Tree Nuts, Peanuts, Wheat, and Soy. Any patients with food allergies or intolerance to potential components of EatWell meal kits will be excluded from participation to avoid any risk of allergic reaction to any of the meals. Therefore, this study poses minimal risk to participants.

We will obtain approval from the Boston Children's Institutional Review Board (IRB) for each of the aims, and we will participate in their standard annual continuing review process. We will also require that all staff and investigators working on this project complete human subjects research training. We will establish a data safety and monitoring board (DSMB) that will meet every 4 months. We will include experienced clinical trial researchers who are independent experts outside of our research team, in addition to [name], [name] and [name]. The Principal Investigator, [name], will be responsible for monitoring the safety of this study. [name] will promptly report adverse events and other study-related information to the IRB. Clinical staff at the health center will be directed to report any suspected events related to this research to [name]. Protocol deviations will be reported to the IRB, along with an annual status report as per IRB guidelines. Adverse events are not anticipated for this study given the low-risk nature of the proposal.

DATA MANAGEMENT METHODS

All study data will be stored on password-protected computers and identified with study IDs. Analytic data files will contain no identifying information. No study report will allow identification of individual participants. Individual patient data collected as part of the intervention surveys or interviews will be kept confidential. Access to identifiable information will be strictly limited to study personnel who require such information to complete the work (e.g., study physician and research coordinator). Whenever possible, printed materials that contain identifying information (e.g. thank you letters) will contain no information revealing diagnoses, treatment, or other clinical information. All study staff will have CITI certifications and will be trained in IRB protocols.

STATISTICAL POWER AND SAMPLE CONSIDERATIONS

STATISTICAL DESIGN

We will use a randomized, cross-over trial study design. We also chose this design because it provided a randomized control trial method. Participants will be individually randomized to one of two intervention sequences:

- A) Meal kit intervention without delay followed by newsletter + pantry referral (standard of care)
- B) Newsletter + pantry referral followed by meal kit intervention after a delay of 8 weeks

Each group will receive 6 weeks of meal kit delivery and will be observed in the study for a total of 14 weeks.

POWER

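### Do six primary feasibility outcomes with no stated metric, denominator or named data source call for a change to the plan?

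*Combined protocol and SAP*

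**What the plan says.** All references are to the combined protocol and SAP.

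- **Study Outcomes** lists the primary domains as "feasibility of recruitment, randomization, retention, adherence, protocol, and assessments". On timing it says "Primary outcomes will be assessed throughout the study", whereas secondary outcomes are tied to Visits 1 to 3. On the analysis set it says "The primary, intention-to-treat analysis will examine the feasibility of the meal kit delivery intervention".
- **Analysis Plan** describes the analysis as largely descriptive, in keeping with a pilot. Its one explicit summary rule is for the other tier: "We will present secondary outcomes as means (with standard deviations) or proportions". It also says that EHR data will be collected.
- **Intervention** states that "EatWell meal kits will be delivered once weekly to households for 6 weeks".
- **Study Visits** and its table, "Table 1. Outline of study visits and measures collected", give the visit content. At V1 staff "review eligibility criteria and obtain informed consent". Later, "Follow-up visits will include dietary assessments and questionnaires", together with weight and height.
- **Adverse Event Criteria and Reporting Procedures** sends protocol deviations to the IRB. **Data Management Methods** mentions surveys or interviews without describing them.
- **Power** refers to feasibility goals but states none, and says the results will inform a larger trial.

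**The concern.** The secondary outcomes have a summary rule and a visit schedule. The primary ones have neither, which is the reverse of the usual order. A descriptive proportion still needs a numerator and a denominator, and adherence to a six-kit programme can be defined in several ways that give different figures.

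The sharper worry is about data. Table 1 shows no count of families approached or declining, and no weekly record of kits received. The first listed contact is V1, so a family that refuses earlier would leave no trace in the listed measures. If kit receipt were asked only at visits, a dyad that missed the visit after its kits would have no adherence value, and the rate among attenders would be too high if leavers had received fewer kits. Definitions can be written later, but unrecorded counts cannot be recovered. Uptake and adherence are also what the larger trial would most want from this pilot.

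**Working it through.** **The plan's own figures.** No feasibility rate, target or precision is stated, so there is none to reproduce. The design figures agree with each other: 8 weeks' delay + 6 weeks of kits = 14 weeks of observation, and 30 households × 6 kits = 180 planned kits.

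**Domain by domain, what the text supports.**

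| Domain | Source in the text | Left unstated |
|---|---|---|
| Recruitment | Eligibility review and consent at V1; EHR data; routine food-insecurity screening at the one recruiting health center | Log of approaches; denominator |
| Randomization | Individual randomization of 30 dyads | Metric |
| Retention | Attendance at V2 (6 weeks) and V3 (14 weeks) | Which visit is the main one |
| Adherence | Six weekly deliveries; unspecified questionnaires, surveys or interviews | Delivered or used; source |
| Protocol | Deviations reported to the IRB | Metric |
| Assessments | Forms and measurements at V1 to V3 | Metric |

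The gap is real. It consists of silence, and no stated rule is wrong. Table 1 outlines visit measures, and a screening log or a delivery record would not normally appear in such a table.

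**How far the definition moves adherence (assumed counts).** Suppose 20 households take 6 kits, 4 take 5, 3 take 3 and 3 take none.

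- Kits taken: (20×6 + 4×5 + 3×3 + 3×0)/180 = 149/180 = 83%
- All six kits: 20/30 = 67%
- At least five: 24/30 = 80%
- Any kit: 27/30 = 90%

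The spread is 67% to 90%. A table of kits per household, the natural descriptive display for 30 dyads, yields all four figures.

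**How far the time point moves retention (assumed counts).** 27/30 = 90% at V2 and 24/30 = 80% at V3. Reporting both visits settles it.

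**What missing kit records would cost.** If m of 30 dyads have no record and the rest average r, the mean over all 30 lies between (30 − m)r/30 and that value plus m/30. For m = 3 and r = 5.4/6 = 0.90, the lower bound is 27×5.4/180 = 145.8/180 = 81% and the upper bound is (145.8 + 18)/180 = 91%. The width is 3/30 = 10 points; for m = 6 it is 20 points. This holds for any study of 30 units. Nothing in the document informs m, and nothing says that kit receipt is asked only at visits. Even if it were, sequence A receives its kits before V2 and could still be asked at V3.

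**Precision at this size.** Exact 95% intervals are 61% to 92% for 24/30 and 73% to 98% for 27/30. These describe a sample of 30 and are not evidence of the alleged defect.

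**Unit of analysis.** Treating 180 kits as independent gives 162/180 = 90% (85% to 94%), against 73% to 98% for 27/30 dyads. The two are comparable only if each household takes all six kits or none. For a dyad mean of 0.90 the interval is 0.90 ± 2.045 × SD/√30. With an assumed SD of 0.10 that is 0.863 to 0.937; with 0.20 it is 0.825 to 0.975. Summarising by dyad is right in principle, but the size of the contrast depends on an unknown SD, and the plan nowhere proposes to analyse kits as independent.

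**The case for a change.** The best case for a change is that feasibility is the primary question, the remedy costs a few lines and two simple logs, and refusals that go unrecorded are gone. The intention-to-treat label cannot rescue recruitment, because families are approached before they are randomised. The general statement that primary outcomes are assessed throughout is a window and gives no outcome its own time point.

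Most of this is fair as description. It stands that no domain has a definition, that no source is named for recruitment or adherence, and that the intention-to-treat label fits only domains measured after randomisation.

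The step from silence to lost data does not stand. A team that has declared recruitment and adherence to be primary outcomes, assessed throughout, has to record them in order to follow its own plan. The document does not say whether the meal kit company passes its delivery records to the study, and that silence is no evidence that it does not. For recruitment, consented over approached does need a count of approaches. Enrolment per month does not, and the EHR might give a rough eligible pool afterwards, although household size and delivery area may not be in it.

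The obvious replacement for adherence is itself debatable. Kits delivered out of six largely measures the delivery service, since a household can receive six kits and cook none.

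**Conclusion.** The omission is confirmed, but it does not call for a change. It is missing detail of the kind that analysts fill sensibly in a descriptive pilot: participant flow from approach to V3, attendance and form completion by visit and sequence, kits per household, and deviations. No stated rule produces a wrong figure. No feasibility threshold exists that one definition would pass and another fail.

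The definitional spread (67% to 90% in the assumed data) disappears once the kit distribution is shown. The m/30 loss is zero if every household has a delivery record, and it reaches 10 or 20 points only for an assumed 3 or 6 dyads without one.

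The conclusion rests on one assumption: that listing recruitment and adherence as primary outcomes, assessed throughout the study, means that approaches and deliveries are recorded. Nothing in the document contradicts this. If neither were being recorded, the data-loss argument would become real, but that would be a failure to follow the plan as written.

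### Does an allergy exclusion limited to the enrolled child and parent fall short of the protocol's safety statement when kits go to whole households?

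*Combined protocol and SAP*

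**What the plan says.** Under DESIGN, the exclusion criteria begin "Participants (either child or parent) with a history of", and the first item is "food allergies or intolerance to dairy, gluten, soy, or any potential component of the meal kit". The inclusion criteria define participants as the dyad and require that the child live "in a household of ≤ 5 people". The Intervention paragraph adds: "Each household will receive one meal kit per week". At visit 1 the study physician and research assistant review eligibility, and Table 1 lists "Medical history: to assess for underlying gastrointestinal, endocrinologic, cardiometabolic, allergic conditions, and current and past medication history".

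ADVERSE EVENT CRITERIA AND REPORTING PROCEDURES describes the kitchen's food-safety controls and then the kits. They sometimes contain gluten and dairy, "but do not contain tree nuts or peanuts, although they are manufactured in a shared use facility", and eight allergens may be present in traces. The next sentence says that patients allergic to, or intolerant of, possible kit components "will be excluded from participation to avoid any risk of allergic reaction to any of the meals". The section then concludes that the risk to participants is minimal.

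**The concern.** Two things look wrong.

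The first is who is covered. The kit goes to a household, household size is an entry criterion, and the Analysis Plan says "we will collect secondary outcomes including severity of household food insecurity and child BMI". It is natural to suppose that siblings and other adults eat the meals. Nothing in the file asks about their allergies, yet the safety section speaks of avoiding any risk from any meal.

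The second is what is covered. The criterion names dairy, gluten and soy and then uses a catch-all that is not defined. The safety section says that the kits contain no peanuts or tree nuts but may carry traces of both. One screener might exclude a peanut-allergic child because of the traces, and another might enrol the child because peanuts are not an ingredient.

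If both points held, a stated ground for calling the meals low risk would be weaker than it reads, and eligibility could be applied unevenly.

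**Working it through.** The plan gives no statistical figure on this point, and the sample of 30 dyads rests on practical considerations. The check is therefore a head count and a comparison of the texts.

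**Head count.** Inputs: 30 dyads (Sampling/Power), 2 enrolled people per household, at most 5 people per household (Inclusion Criteria), 6 weekly kits (Intervention).

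- People outside the exclusion = 30 × (household size − 2).
- Size 2: 30 × 0 = 0. Size 3: 30 × 1 = 30. Size 4: 30 × 2 = 60. Size 5: 30 × 3 = 90.
- At the maximum, 90 of 150 household members (60%) are not covered. At the minimum, none are left uncovered. The documents give no household-size distribution.
- Deliveries: 30 × 6 = 180. Person-weeks for people outside the dyad: 0 to 90 × 6 = 540.

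**Chance that an allergic person is present.** This needs a prevalence that the documents do not give. Assume p between 1% and 10% and use 1 − (1 − p)^n.

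| Others in the trial, n | p = 1% | p = 10% |
|---|---|---|
| 30 | 26.0% | 95.8% |
| 60 | 45.3% | 99.8% |
| 90 | 59.5% | above 99.9% |

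These figures give the chance that at least one such person lives in some household. They are not the chance of a reaction, because the documents do not say who eats the kit or how often an allergen is in it.

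**Who the sentence is about.** Its subject is patients excluded from participation, and the conclusion drawn from it concerns participants. The inclusion criteria define participants as the dyad. On that reading the sentence gives the purpose of the exclusion and makes no promise about anyone else. The criterion says child or parent where the safety section says patients. That is a difference of wording, and nothing suggests that a second rule is meant.

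**What the catch-all covers.** The eight trace allergens divide as follows.

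- Three are reached by the criterion's named items: milk through dairy, wheat largely through gluten, and soy.
- Five depend on the catch-all: eggs, fish, shellfish, peanuts and tree nuts. For peanuts and tree nuts, the safety section says the kits do not contain them. For the other three it says nothing about ingredients.

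Two features of the text favour counting traces. The exclusion sentence comes directly after the trace list and refers to possible components. Soy is a named exclusion, although the safety section mentions it only as a possible trace. Neither is conclusive, since the account of ingredients may be incomplete. Together, with a physician taking part in the eligibility review, they make the inclusive reading the likely one in practice.

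**Effect on the analysis.** Eligibility is reviewed at visit 1 and applies alike to both sequences. Either reading changes who may enter. Neither changes how the sequences are compared or how feasibility is summarised.

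**Cost of screening the household.** Suppose that an allergy in any other member made a family ineligible. With k other members, the share of families lost is 1 − (1 − p)^k under the same assumed p.

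- k = 1: 1% to 10%.
- k = 2: 2% to 19%.
- k = 3: 3% to 27%.

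At the top of the range, 0.27 × 30 is about 8 families in every 30 approached. Feasibility of recruitment is a primary outcome.

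**The case for a change.** The strongest case for a change is that the trace question concerns enrolled children and does not depend on who else eats the meals. An eligibility criterion should not have to be inferred from sentence order, and a defining clause would cost almost nothing. The safety argument also leans on this exclusion, Table 1 lists no specific question about reactions at visits 2 and 3, and the file does not say how a reaction in a non-enrolled relative would reach the investigator.

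Part of this stands. The catch-all is undefined, and the any-risk wording is more absolute than a history-based rule for two people can support. The rest carries less weight. The exclusion is one of several stated grounds for low risk, alongside the food-safety programme, regulatory compliance and city inspection. Reaction questions are a matter of adverse-event capture, for which the protocol already provides investigator monitoring, staff reporting and a DSMB. The visit questionnaires are not itemised, so it cannot be said that they omit the topic. Allergen information for families may be in the consent pages, which are not in the public file, so its absence here cannot be counted against the plan.

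**Conclusion.** No change to the plan follows. The observations are correct, but they amount to an undefined term and a loosely absolute phrase. The household point contradicts nothing in the protocol, because both the exclusion and the minimal-risk conclusion are confined to the dyad. It also rests on the inference that others eat the kits. The trace point is a gap in definition that the surrounding text largely settles and that the physician at visit 1 can be expected to fill sensibly.

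The size is 0 to 90 people outside the exclusion, depending on household sizes that are not given, and five of eight trace allergens that depend on the catch-all. The probabilities above rest wholly on an assumed prevalence of 1% to 10% and are not evidence of harm. Softening the any-risk phrase would alter nothing the trial does. Asking about people who are not enrolled is a trade-off for the sponsor and the IRB, with a possible recruitment cost of 1% to 27% of families under the same assumption. The sample size, the randomisation, the descriptive analysis and the minimal-risk statement for participants all stand.

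### The only route described for an adverse event to reach the investigator is a report from health-center staff; no adverse-event question is described at V2 or V3

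*Combined protocol and SAP*

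**What the plan says.** The section on adverse event criteria and reporting procedures gives the Principal Investigator responsibility for monitoring safety. It says that the investigator "will promptly report adverse events and other study-related information to the IRB". It provides for a DSMB meeting every 4 months and for IRB continuing review. On how an event becomes known, it says: "Clinical staff at the health center will be directed to report any suspected events related to this research". The recipient's name is masked in this copy; the adjacent sentences indicate the investigator. The section calls the study minimal risk and does not expect adverse events.

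Under Study Visits, the two follow-up visits are "conducted between Periods 1 and 2 (6 weeks), and then after Period 2 (14 weeks"). Their content is given as: "Follow-up visits will include dietary assessments and questionnaires and measure" the children's weight and height. Table 1 lists the same three things at both visits: dietary assessment, questionnaires and anthropometrics. On staffing it says "V2, in-person: Participants will meet with the research assistant" and "V3, in-person: Participants will meet with the study physician and research assistant".

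Under Sampling/Power: "The planned sample of 30 dyads (a total of 30 children + 30 caregivers"). Under Statistical Design: "Each group will receive 6 weeks of meal kit delivery and will be observed in the study for a total of 14 weeks".

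**The concern.** The kits go to households and are prepared there, so any problem with them would first appear away from the clinic. The described route works only if the family brings the event to the health center and staff there suspect a link to the research. It has three gaps:

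- an event managed at home or at another facility;
- an event seen by health-center staff but not linked to the study;
- an event in the caregiver. The children are drawn from the clinic's primary care patients, but the caregivers are not stated to be patients there.

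What is at stake is the completeness of the safety information that the investigator, the IRB and the DSMB receive. The results will also be used to refine the intervention for a larger trial. If no events are reported, a reader of the pilot could not tell whether none occurred or nobody asked.

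**Working it through.** The plan states no figure on this point, so there is none to reproduce. The check is to take each element of the protocol that could bring an event to light and see whether the text gives it that task.

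- **Health-center staff** (adverse event section): yes, for suspected events related to the research.
- **Investigator** (same section): responsible for safety overall, with no method of finding events stated.
- **IRB reporting** (same section): outgoing. It passes on events already known.
- **DSMB** (same section): meets every 4 months, with no event-collection step stated.
- **V2** (Study Visits, Table 1): research assistant only, with no adverse-event question listed.
- **V3** (Study Visits, Table 1): the study physician is present, but no adverse-event question is listed.
- **Questionnaires and assessments** (Study Outcomes): the named topics are food insecurity, diet quality, mealtime behaviors and perceived stress. None concerns adverse events, but the instruments are not itemised.
- **EHR data** (Analysis Plan): to be collected and described, with no stated safety use.

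Only the first is an inbound route. Its reach against the people and time observed is as follows.

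1. People enrolled: 30 children + 30 caregivers = 60. Caregivers are 30/60 = 50%. The plan does not place this half within the view of health-center staff.
2. Planned kits: 30 households x 6 weekly deliveries = 180 at most, all used at home.
3. Intervals between visits: V1 to V2 is 6 weeks, and V2 to V3 is 14 - 6 = 8 weeks. A question at V2 and V3 would therefore cover the full 14 weeks for a dyad that attends both.
4. Opportunities to ask: 30 dyads x 2 visits = 60 in-person contacts at most, all already planned.

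Steps 1 and 2 describe who and what the route has to cover. They are not estimates of missed events.

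**The case against.** The strongest case against is one of proportion. The protocol gives reasons for its minimal-risk description: a food-safety program, city inspection, and exclusion of either child or parent with relevant allergy or intolerance. Oversight includes independent DSMB members and annual IRB review. Safety is not an outcome, and nothing in the text is contradictory or miscalculated. Table 1 is an outline, and the data management section mentions surveys or interviews whose content is not shown. Families meet study staff in person twice after baseline, with a physician present at V3. Consent pages, absent from this copy, may tell families how to report a problem.

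Most of this stands. It limits the claim to what the protocol describes, not what will be done, and it argues for a small remedy. It does not remove the gap. Exclusions and food-safety controls lower the expected number of events, and the DSMB and IRB review what reaches them; neither finds events. A pilot meant to test procedures for a larger trial is also a natural place to test this one.

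A reader might infer more than the text supports:

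- **That a kit-versus-newsletter safety comparison is biased.** Staff may be readier to suspect a link during kit weeks, but the plan makes no such comparison and no figure in it shows differential capture.
- **That the under-reporting can be quantified.** That would need the share of events that reach the staff, which the documents do not give.
- **That events in sequence B would be assigned to the wrong weeks.** That could arise only if events were collected by visit window without dates, and the plan has no such scheme.

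**Conclusion.** The point holds as a gap in the described ascertainment of adverse events. Followed as written, the protocol relies on one route, which can miss events handled at home or elsewhere, events not linked to the study by staff, and events in caregivers, who are half of those enrolled. A report of no events would then be hard to interpret. How many events might be missed cannot be stated from the documents.

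It would be wrong to read this as saying that safety is unmonitored: responsibility, IRB reporting and a DSMB are all in place. The feasibility outcomes, the sample of 30 dyads and the descriptive analysis are untouched. The conclusion rests on two assumptions: that the staff report goes to the investigator, and that neither the questionnaires nor the consent material already asks families about adverse events. If either instrument does so, only a clarification is needed. Confidence is medium for that reason. This is a cheap improvement that should be made.

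**What to change.** In Table 1, add one standard adverse-event question at V2 and V3. Ask it in the same words in both sequences, about the enrolled child and the enrolled caregiver, whatever the suspected cause, and record the onset date. State that the answers go to the investigator, including those taken at V2 by the research assistant, and that the existing IRB and DSMB route then applies. Keep the staff reporting alongside it, and report simple descriptive counts. If the questionnaires already contain such a question, name the item in Table 1 and change nothing else.

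The cost is a little more time at up to 60 visits that are already planned, plus the work of processing events, many of them unrelated to the kits. Recall over 6 to 8 weeks will be imperfect, and a dyad that misses V3 is not covered after its last visit. Sample size, randomization, eligibility and outcomes do not change.
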